7.5 Duration of Follow-Up

Study follow-up and evaluations are outlined in the study calendar (Appendix D). The total length of follow-up will be 18 months from the start of treatment (day 1).

Assessments required within 30 days prior to HCT will be completed as per institutional protocols and should include a physical exam, medical history, pregnancy test (women of childbearing potential), CBC, serum chemistry, and bone marrow biopsy or aspirate for morphology.

At Day 100 post-HCT (+/- 14 days), EORTC-QLQ-C30 and EORTC-QLQ-HDC29 quality-of-life measures will be collected.

7.6 Dosing Delays/Dose Modifications

For patients who are enrolled on subsequent treatment protocols, the strategy for managing situations that require dosing delays or modifications, e.g. if the subject's marrow has not recovered to acceptable levels for the next cycle of therapy will be determined by the subsequent treatment protocol.

For patients who are not enrolled on other treatment protocols, the management of situations that require dosing delays or modifications should be carried out according to institutional practice guidelines or the preference of the attending physician.

7.7 Criteria for Removal/Withdrawal

A patient must be discontinued from protocol-prescribed therapy under the following circumstances:

- Consent withdrawal at the patient's own request or at the request of their legally authorized representative;
- Any event that, in the judgment of the Investigator, poses an unacceptable safety risk to the patient;
- If, in the investigator's opinion, continuation in the study would be detrimental to the patient's well-being;

- Significant deviation from inclusion/exclusion criteria, in the opinion of the investigator;
- A positive pregnancy test at any time during the study;
- An intercurrent illness that, in the judgment of the investigator, would affect assessments of the clinical status to a significant degree and requires discontinuation of therapy, or
- Completion of the study

Once the attending physician has met and discussed the decision with the patient and/or family member, the Notice of Withdrawal from a Research Study form (see Appendix E) should be filled out. Complete this form only when the patient has withdrawn consent.

- It is the responsibility of the PI or his/her designee to complete the Notice of Withdrawal From a Research Study Form and fax it to the FHCRC Research Coordinator at [contact].

Study treatment is defined as "any activity involving a patient or donor described in a protocol that is not part of their routine medical care". Patients who withdraw from study treatment will be asked permission to continue to collect and record survival data up to the protocol-described end of the subject follow-up period.

Patients who are withdrawn from the protocol will not be replaced as this is intent to treat analysis.

8.0 Adverse Event Reporting

Adverse events will not be reported as all AEs and SAEs that occur are considered to be related to treatment and would be considered "expected" side effects from standard of care treatment for either study arm. If patients are enrolled on an additional treatment protocol where they will receive an investigational drug, please refer to that protocol for a list of expected adverse events and event-capture procedures.

Patients who are not enrolled on this protocol who are not enrolled on an additional protocol, will receive standard therapies with FDA-approved medications. Please refer to the package insert of those medications for a listing of specific expected adverse events.

Death will be reported at the annual continuing review if it occurs within the participant's 18-month study participation period.

After the completion of treatment, patients will be tracked for progression and survival during the patient's 18-month study participation.

Outside sites will be required to report all deaths to the coordinating center that occur during subjects' 18-month participation period. Outside sites will communicate deaths to the coordinating center by email or fax. The coordinating center will maintain a death log for all protocol participants.

9.0 DATA AND SAFETY MONITORING PLAN

The principal investigator (PI) of the study will have primary responsibility for ensuring that the protocol is conducted as approved by the FHCRC Scientific Review Committee and Institutional Review Board. The PI will ensure that the monitoring plan is followed and that all data required for oversight of monitoring are accurately reported to the FHCRC/UW Cancer Consortium Data and Safety Monitoring Committee (DSMC)... Once per month, the PI will personally review with the Research Nurse the clinical status of all the enrolled patients.

Under the provisions of the DSMP, the Cancer Consortium Clinical Research Support (CRS) team provides monitoring for quality process and compliance by qualified monitors unaffiliated with the

conduct of the study. Monitoring visits occur at specified intervals determined by the FHCRC DSMC assessed risk level of the study and the findings of the previous visit.

An annual review of the progress of the study with respect to the monitoring plan will be performed by the DSMC. The DSMC reviews accrual, serious adverse events, stopping rules and adherence to the protocol-specific data and safety-monitoring plan.

10.0 STUDY AGENT INFORMATION

Patients enrolled in this study may receive different treatments under each of the study arms. If enrolled on a treatment protocol, please refer to that protocol for information regarding information regarding obtaining, handling and accounting for the study agent and whether the study agent is provided by the study.

If the patient is not enrolled on a treatment protocol, the agent will be obtained and handled through the pharmacy where the patient is receiving care. The study agent will not be provided by the study.

11.0 ASSESSMENT OF EFFICACY

11.1 Efficacy Parameters

The primary outcome is 18-month failure-free survival (failure defined as death or relapse).

Relapse will be as defined by the International Working Group (IWG) response criteria in myelodysplasia (Cheson, et. al., Blood 2006;108:419.). Please see Appendix B for a table defining the response criteria for this study. Response criteria are determined by a morphologic count of the myeloblast population on aspirate smear. If an aspirate cannot be obtained, myeloblast percentage should be determined by morphologic and/or immunohistochemical staining of the bone marrow biopsy or alternatively determined by flow cytometry of a decalcified bone marrow biopsy sample.

11.2 Method and Timing of disease burden assessment

The results of a bone marrow biopsy/ aspirate obtained for clinical purposes within 60 days of the start of treatment will be used to establish a baseline prior to the start of treatment. For patients enrolled on concurrent treatment protocols, timing of response assessment will be as outlined by the protocol and will take precedence over the following treatment response assessment guidelines.

If at any point a patient is suspected to have disease progression, a bone marrow biopsy or aspirate may be obtained for clinical purposes to document this progression. For patients who are receiving decitibine-based therapy under Arm A, it is recommended that a bone marrow biopsy or aspirate be obtained after 2 to 4 cycles to evaluate response. For patients who are receiving azacitidine-based therapy under Arm A, it is recommended that a bone marrow biopsy or aspirate be obtained after 4 to 6 cycles to evaluate response.

For patients randomized to Arm B, response to therapy will be determined by bone marrow biopsy or aspirate 28 (+/- 3) days after the start of therapy or at the time of count recovery.

A bone marrow biopsy/ aspirate will be obtained prior to HCT as per institutional protocol (standard practice).

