4.2 Endpoints

4.2.1 Primary Endpoint

18-month failure-free survival (failure defined as death or relapse)

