APPENDIX C**Response Criteria**

Category	Response criteria (responses must last at least 4 wk)
Complete remission (CR)	Bone marrow: \leq 5% myeloblasts with normal maturation of all cell lines
Partial remission (PR)	All CR criteria if abnormal before treatment except: - Bone marrow blasts decreased by \leq 50% over pretreatment but still $>$ 5% - Cellularity and morphology not relevant
Stable disease (SD)	Failure to achieve at least PR, but no evidence of progression
Disease Progression (DP)	For patients with: - Less than 5% blasts: \geq 50% increase in blasts to $>$ 5% blasts - 5%-10% blasts: \geq 50% increase to $>$ 10% blasts - 10%-20% blasts: \geq 50% increase to $>$ 20% blasts - 20%-30% blasts: \geq 50% increase to $>$ 30% blasts
Relapse after CR or PR	At least 1 of the following: - Return to pretreatment bone marrow blast percentage - Decrement of \geq 50% from maximum remission/response levels in granulocytes or platelets - Reduction in Hgb concentration by \geq 1.5 g/dL or transfusion dependence

From: Cheson, BD, et al. Blood. 2006;108:419-425.

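### Relapse counts only after a documented response, and the marrow that documents it is set at about week 4 in Arm B but only recommended, and later, in Arm A, so an early lost response can be a failure in one arm and unrecorded in the other

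*Combined protocol and SAP*

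**What the plan says.** Section 4.2.1 gives the primary endpoint as "18-month failure-free survival (failure defined as death or relapse"). Section 11.1 adds: "Relapse will be as defined by the International Working Group (IWG) response criteria in myelodysplasia". It also says "Response criteria are determined by a morphologic count of the myeloblast population on aspirate smear". The criteria table is in Appendix C, although Section 11.1 points to Appendix B.

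In that table the only relapse row is "Relapse after CR or PR". Stable disease and disease progression are separate rows, and neither is a failure under Section 4.2.1. The table heading adds that "responses must last at least 4 wk".

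Section 11.2 (repeated in Section 7.4) sets the response marrow differently by arm:

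- **Arm B:** "response to therapy will be determined by bone marrow biopsy or aspirate 28 (+/- 3) days after the start of therapy", or at count recovery.
- **Arm A, azacitidine:** "it is recommended that a bone marrow biopsy or aspirate be obtained after 4 to 6 cycles to evaluate response".
- **Arm A, decitabine:** also a recommendation, after 2 to 4 cycles.

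The Appendix D footnote recommends a marrow after 6 HMA cycles for a patient who has had none since screening. The plan thus foresees that an Arm A patient may reach that point without one.

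Three provisions can bring an earlier marrow. A concurrent treatment protocol's timing takes precedence, a marrow may be taken when progression is suspected, and the pre-HCT work-up in Section 7.5 includes "bone marrow biopsy or aspirate for morphology" in either arm.

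Section 13 defines success as an observed 18-month failure-free rate with HMA no lower than that with IC. It gives no margin and no test.

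**The concern.** A patient cannot relapse, for the purpose of the endpoint, until a response has been recorded. Because the marrow that records it is firm and early in one arm and advisory and later in the other, the opportunity to observe the event differs by arm. This concerns patients who did respond. It is a separate matter from progression lying outside the failure definition.

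Consider a marrow response present at week 4 and lost by week 14, followed by other therapy and HCT, with the patient alive and disease-free at 18 months. In Arm B the day-28 marrow can record the response, and its loss can then be a relapse and a failure. In Arm A on azacitidine the first recommended marrow comes after the loss. It reads as stable disease or progression, and the patient is failure-free.

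The direction favours HMA, the arm that needs only to tie. The plan's success probabilities take no account of such a difference, so part of an observed success could reflect when marrows were taken.

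**Working it through.** **1. When a relapse first becomes countable.** Inputs: the marrow times in Section 11.2, the suggested azacitidine cycle of 28 (+/- 3) days in Section 7.1, the 4-week minimum in Appendix C, and 18 months taken as 78 weeks. No decitabine cycle length is given, so 28 days is assumed. Formula: first marrow (weeks) = cycles x 28 / 7. Earliest countable relapse = first marrow + 4, if the response is dated from the marrow that first shows it.

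| Regimen | First response marrow | Earliest countable relapse | Share of 78 weeks |
|---|---|---|---|
| Arm B | week 4 (25 to 31 days = 3.6 to 4.4), or count recovery | 4 + 4 = week 8 | 8/78 = 10% |
| Arm A, decitabine | 2 to 4 cycles = week 8 to 16 | week 12 to 20 | 15% to 26% |
| Arm A, azacitidine | 4 to 6 cycles = week 16 to 24 | week 20 to 28 | 26% to 36% |

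With the +/- 3 days applied to every cycle, the azacitidine marrow falls between 4 x 25 / 7 = week 14.3 and 6 x 31 / 7 = week 26.6. An earlier marrow under any of the three provisions shortens the gap.

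**2. How the loss is seen.** Once a response is on record, Appendix C accepts a return to the pretreatment blast percentage, a fall of at least 50% in granulocytes or platelets, a haemoglobin drop of at least 1.5 g/dL, or transfusion dependence. The loss therefore does not need another marrow. The step that differs by arm is recording the response.

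**3. The plan's own probabilities.** With X_HMA and X_IC independent binomial counts of failure-free patients, n = 30 each, P(success) = P(X_HMA >= X_IC).

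| HMA, IC | Section 13 | Exact |
|---|---|---|
| 50%, 30% | 0.96 | 0.959 |
| 45%, 30% | 0.91 | 0.911 |
| 50%, 60% | 0.26 | 0.257 |

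All three reproduce.

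**4. Sensitivity to unequal detection.** The documents do not give the number k of patients per 30 who are alive at 18 months and whose only failure is an early lost response. It is an assumption, shown from 0 to 3. Take 40% as the HMA rate and as the IC rate under equal ascertainment. The Arm B schedule then counts k extra failures, so the counted IC rate is 0.40 - k/30.

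| k | Counted IC rate | P(success) |
|---|---|---|
| 0 | 40.0% | 0.552 |
| 1 | 36.7% | 0.655 |
| 2 | 33.3% | 0.749 |
| 3 | 30.0% | 0.830 |

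Treating the same patients as failures missed in Arm A (HMA counted at 0.40 + k/30, IC at 40%) gives 0.653, 0.743 and 0.820 for k = 1, 2, 3. In the plan's unfavourable case (HMA 50%, IC 60%), subtracting k/30 from the IC rate moves 0.26 to 0.35, 0.45 and 0.55.

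**The case against.** The strongest reply is that the mechanism needs a narrow course. The Arm A patient must respond early, hold the response for at least 4 weeks, lose it before any marrow is taken, and be alive at 18 months without a later countable relapse. Deaths count alike in both arms. Nothing in the documents shows that any azacitidine patient follows this course, and zero is compatible with the text. This stands, and it is why the figures are only an illustration.

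A reader might infer that the same lost response always fails in Arm B and never in Arm A. The documents do not support that. A single day-28 marrow cannot show that a response lasted 4 weeks, and Arm B has no scheduled marrow to confirm it or show its loss unless re-induction or HCT follows. Detection of the loss in Arm B is largely clinical. In Arm A, a concurrent protocol, a for-cause marrow or an early pre-HCT marrow can record the response.

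A reader might also take week 4 against week 24 as the contrast. That ignores the 4-week minimum, the count-recovery alternative in Arm B and the shorter decitabine interval.

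These points limit the size and reach of the bias. None makes the schedules equal, and no text says how to classify a patient whose response was never documented.

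**Conclusion.** The point holds as a difference in the opportunity to detect relapse, running toward HMA. Its source is the wording of Sections 4.2.1, 11.1 and 11.2 with Appendix C. If each Arm A response is first seen at the recommended marrow, the earliest countable relapse is 12 to 20 weeks later with azacitidine than in Arm B, and 4 to 12 weeks later with decitabine at an assumed 28-day cycle.

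The effect on the conclusion is unknown because k is unknown. With no margin in the success rule, even one such patient in 30 would move the probability of success by about 0.10 when the arms are equal at 40% under equal ascertainment. The documents do not support saying that an HMA success would be produced by the marrow schedule, only that the planned analysis could not rule out a contribution. The issue should be addressed in the analysis plan; confidence is medium.

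**What to change.** In Section 13, keep the primary endpoint and pre-specify:

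1. **Overall survival companion.** The same benchmark comparison on 18-month overall survival, by intention to treat. Its ascertainment does not depend on marrow timing. Survival at 18 months is already in Appendix D, and Section 8.0 already requires outside sites to report deaths.
2. **Restricted-relapse sensitivity analysis.** Count death at any time, plus relapse documented after the pre-HCT marrow or, in patients not transplanted, after week 24. State that this reduces but does not remove the dependence on the Arm A marrow and on HCT timing. A relapse after week 24 still needs a recorded response, and the date of HCT may itself differ by arm.
3. **Interpretation.** Describe an HMA success as robust to assessment timing only if the benchmark is also met in both analyses.
4. **Table by arm.** Report the date of the first response marrow and the number of failures that are pre-HCT relapses.

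Costs: the companion analyses have fewer events. Marrow, response and relapse dates must be abstracted from the clinical record, including at outside sites, because the Appendix H sheet has no fields for them. No marrow is added and no clinical rule changes.

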11.3 Quality of Life Assessment

Quality of life will be assessed using the EORTC QLQ-C30 questionnaire and the QLQ-HDC29 module (Appendix G) at the following timepoints:

- EORTC QLQ-C30 questionnaire at the time of screening
- EORTC QLQ-C30 & QLQ-HDC29 at the completion of initial therapy prior to transplant
- EORTC QLQ-C30 & QLQ-HDC29 at 100 (\pm 14) days after stem cell infusion (Day +100)

The QLQ-C30 is a validated and widely used questionnaire to assess quality of life in cancer patients. The QLQ-HDC29 is treatment-specific quality of life questionnaire to QLQ-C30), that addresses treatment-specific side effects as well as emotional, social, and family issues for patients treated with high-dose regimens and HCT. The QLQ-HDC29 module is targeted to cover time during the treatment and up to 6 months post-treatment.

The QLQ-C30 is composed of both multi-item scales and single-item measures. These include five functional scales, three symptom scales, a global health status / quality-of-life scale, and six single items. Each of the multi-item scales includes a different set of items - no item occurs in more than one scale.

All of the scales and single-item measures range in score from 0 to 100. A high scale score represents a higher response level.

When the Quality of Life questionnaires are scored, the principle for scoring these scales is the same in all cases:

1. Estimate the average of the items that contribute to the scale; this is the raw score.
2. Use a linear transformation to standardize the raw score, so that scores range from 0 to 100; a higher score represents a higher ("better") level of functioning, or a higher ("worse") level of symptoms.

The QLQ-HDC29 module includes 29 items, consisting of 6 multi-item scales and 8 single-items. The scoring algorithms are similar to the scoring for the EORTC QLQ-C30. For the multi-item scales and single-item scales (except item 52) a high score is equivalent to worse or more symptoms/problems. For Spiritual item 52, a higher score indicates positive experience or less problems.

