7.3 Screening

Bone marrow biopsy or aspirate for morphology must be collected within 60 days prior to Day 1 of treatment.

Within 30 days before Day 1 of treatment, perform these assessments

- Complete medical history and physical examination,
- CBC with differential
- Serum Chemistry
- Pregnancy test for women of childbearing potential
- EORTC-QLQ-C30 questionnaire

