13.0 STATISTICAL CONSIDERATIONS

Eligible patients will be randomized in a 1:1 fashion. The primary outcome will be analyzed on an intention-to-treat basis. It is not possible to enroll enough patients to this trial to show a statistically significant difference in overall survival between groups unless the assumed-true difference is unrealistically large. Instead, we have set a benchmark for “success” to be that the observed 18-month failure-free survival with hypomethylating agent-based treatment be at least as high as that in the intensive chemotherapy group. With 30 patients per arm, if the assumed-true survival probabilities are 50% and 30%, respectively, then the probability of observing an 18-month failure-free survival in the HMA group that is at least as high as that in the IC group is approximately 0.96. If the assumed-true probabilities are 45% and 30%, the probability of observing a success is approximately 0.91. On the other hand, if the 18-month failure-free survival in the HMA group and IC group is 50% and 60%, respectively, then the probability of observing a rate in the HMA group that is at least as high as that in the IC group is approximately 0.26.

The quality-of-life questionnaires will be scored. In addition to reporting the absolute scores, a distribution-based interpretation will be conducted using the standardized response mean to analyze changes in scores over time and differences between groups.

**Projected Target Accrual
ETHNIC AND GENDER DISTRIBUTION CHART**

TARGETED / PLANNED ENROLLMENT: Number of Subjects			
Ethnic Category	Sex / Gender		
	Females	Males	Total
Hispanic or Latino	1	1	2
Not Hispanic or Latino	24	34	58
Ethnic Category Total of All Subjects*	25	35	60
Racial Categories			
American Indian / Alaska Native	0	0	0
Asian	0	1	1
Native Hawaiian or Other Pacific Islander	0	0	0
Black or African American	1	1	2
White	24	33	57
Racial Categories: Total of All Subjects*	25	35	60

*The “Ethnic Category Total of All Subjects” must be equal to the “Racial Categories Total of All Subjects.”

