30. How would you rate your overall quality of life during the past week?

1 2 3 4 5 6 7

Very poor

Excellent

EORTC QLQ – HDC29

Patients sometimes report that they have the following symptoms or problems. Please indicate the extent to which you have experienced these symptoms or problems during the past week. Please answer by circling the number that best applies to you.

During the past week:	Not at all	A little	Quite a bit	Very much
31. Have you had soreness in your mouth?	1	2	3	4
32. Have you had a dry mouth?	1	2	3	4
33. Have you had trouble swallowing?	1	2	3	4
34. Did food and drink taste different from usual?	1	2	3	4
35. Have you had abdominal pains or cramps?	1	2	3	4
36. Have you had skin problems (e.g. itchy, dry)?	1	2	3	4
37. Have you been upset by how the treatment has affected your hair?	1	2	3	4
38. Have you worried about your weight being too low?	1	2	3	4
39. Have you had fevers or chills?	1	2	3	4
40. Did you urinate frequently?	1	2	3	4
41. Have you had aches or pain in your bones?	1	2	3	4
42. Have you found it difficult to finish things you started?	1	2	3	4
43. Did you worry about the results of examinations and tests?	1	2	3	4

Please, complete the following questions if you are currently still in hospital for your treatment. If not, please go to question 48 on next page.

During the past week:	Not at all	A little	Quite a bit	Very much
44. Have you had trouble coping with the hospital stay?	1	2	3	4
45. Has the isolation in hospital troubled you?	1	2	3	4
46. Have you worried that the blood (i.e. blood counts) may not recover?	1	2	3	4
47. How satisfied were you with the preparation for your treatment?	1	2	3	4

Please go on to the next page

During the past four weeks:

	Not at all	A little	Quite a bit	Very much
48. Have you felt isolated from those close to you (family, friends)?	1	2	3	4
49. Have you been concerned about disruption to your family life because of your treatment?	1	2	3	4
50. How distressing, do you think, your illness or treatment has been to those close to you?	1	2	3	4
51. Have you felt a need to keep your fears/concerns from family or friends?	1	2	3	4
52. Has your experience helped you to distinguish between important and non-important things in life?	1	2	3	4
53. Were you worried about your health in the future?	1	2	3	4
54. Have you felt physically less attractive as a result of your illness or treatment?	1	2	3	4

Please mark the box, if the next question does not apply to you

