55. Have you been concerned about your ability to have children?	1	2	3	4
--	---	---	---	---

Please, complete the following questions only if you have completed your hospital treatment and are currently at home.

During the past four weeks:

	Not at all	A little	Quite a bit	Very much
56. Did having to take your drugs regularly interfere with your daily life?	1	2	3	4
57. Have you been watching yourself closely for any new symptoms?	1	2	3	4
58. Have you felt less interest in sex?	1	2	3	4
59. Have you felt less sexual enjoyment?	1	2	3	4

2661.00

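### The QLQ-HDC29 has no pre-treatment reading, so its standardized response mean can describe only the transplant period in transplanted patients, not change due to the randomised initial therapy

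*Combined protocol and SAP*

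**What the plan says.** Section 3.2 makes quality of life under IC versus HMA, as initial therapy, a secondary objective. Section 11.3 sets three time points. The first is "EORTC QLQ-C30 questionnaire at the time of screening". The second is "EORTC QLQ-C30 & QLQ-HDC29 at the completion of initial therapy prior to transplant". The third, again with both instruments, is Day 100 (within 14 days) after stem cell infusion. Section 7.3 agrees: the only quality-of-life form in its screening list is the "EORTC-QLQ-C30 questionnaire". Appendix D shows the same pattern.

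Section 13 says the questionnaires will be scored and absolute scores reported, with a distribution-based interpretation "using the standardized response mean to analyze changes in scores over time and differences between groups". It makes no exception for HDC29. It names no time point or population for the between-arm comparison and gives no rule for items that do not apply.

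On the module itself, section 11.3 states: "The QLQ-HDC29 module includes 29 items, consisting of 6 multi-item scales and 8 single-items". In the form in Appendix G, items 44–47 follow the instruction "Please, complete the following questions if you are currently still in hospital for your treatment", and items 56–59 are to be answered "only if you have completed your hospital treatment and are currently at home".

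**The concern.** HDC29 is the module chosen for treatment-specific burden, and the stated question is what the randomised initial therapy does to quality of life. The method that section 13 names for change cannot answer that question for HDC29, because the first HDC29 form is completed after that therapy. A standardized response mean reported by arm would instead describe what happened between the pre-transplant visit and Day 100. It would also be restricted to patients who reached transplant and completed both forms. Transplant frequency is itself a secondary endpoint (section 4.2.2), so that restriction conditions on something the arms may influence. Such a figure could easily be misread as an effect of IC or HMA.

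A smaller gap is that some items are answered only in hospital and some only at home, and the plan does not say how scores depending on them will be handled.

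**Working it through.** **1. Figures in the plan.** No SD, effect size or power is given for quality of life. The plan's only operating characteristics concern 18-month failure-free survival. The exact probability that X_HMA ≥ X_IC, for independent Binomial(30, p) counts, is 0.959, 0.911 and 0.257 against the stated 0.96, 0.91 and 0.26. These reproduce but do not bear on this point. The stated module length also checks: items 31 to 59 make 29.

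**2. Which change scores exist.** The standardized response mean is the mean within-patient change divided by the SD of that change.

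| Interval | QLQ-C30 | HDC29 |
|---|---|---|
| Screening to post-therapy | yes | no (0 of 60) |
| Screening to Day 100 | transplanted only | no |
| Post-therapy to Day 100 | transplanted only | transplanted only |

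The single HDC29 interval begins after the randomised therapy.

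**3. Setting-dependent items.** In hospital: 44–47, 4 items. At home: 56–59, 4 items. Together 8/29 = 27.6%. The remainder is 31–43 (13) plus 48–55 (8) = 21 items, or 20 if item 55, which has its own does-not-apply box, is set aside.

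**4. What the missing baseline costs the between-arm comparison.** The documents give 30 per arm. Assumed here: two-sided α = 0.05, 80% power, differences in SD units, and a baseline–outcome correlation ρ of 0.3 to 0.7.

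- Post-therapy scores only: detectable difference = (1.960 + 0.842) × √(2/30) = 2.802 × 0.2582 = 0.72 SD. The 95% CI half-width is 1.96 × 0.2582 = 0.51 SD.
- Adjusted for baseline (ANCOVA): multiply by √(1 − ρ²).
- Simple difference in change scores: multiply by √(2(1 − ρ)).

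| ρ | ANCOVA | Change score | Power for 0.5 SD, ANCOVA |
|---|---|---|---|
| 0.3 | 0.69 | 0.86 | 53% |
| 0.5 | 0.63 | 0.72 | 61% |
| 0.7 | 0.52 | 0.56 | 77% |

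Power for 0.5 SD with post-therapy scores only is 49%. If 20 per arm complete the form (assumed), 0.89 SD falls to 0.84, 0.77 and 0.63 SD under ANCOVA. At low ρ the change score is worse than no baseline at all, so the gain comes from adjustment rather than from subtracting.

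**5. Does the missing baseline cause bias?** A simulation of the post-therapy comparison (20,000 replicates, 30 per arm, true difference 0.5 SD, ρ = 0.5, complete data) gave a mean estimate of 0.500 SD. The loss is precision.

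**The case against.** The omission has a rationale. Section 11.3 says the module is aimed at the period during treatment and up to six months afterwards, and items 37, 49, 50 and 54 ask about effects of treatment, or of illness or treatment. The QLQ-C30 covers general quality of life at all three time points, including pain and worry. Section 13 never explicitly promises an HDC29 change from before treatment, and quality of life carries no test or decision rule. All of this stands and keeps the point small. It does not remove the mismatch: section 13 applies one change statistic to both instruments, and symptom and worry items such as mouth soreness, fevers, bone pain and concern about test results can be answered at entry.

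Three stronger readings are tempting but unsupported:

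- A reader might infer that HDC29 cannot measure the effect of randomised therapy at all, or that an arm difference cannot be told apart from baseline differences. Section 13 randomises 1:1 and reports absolute scores. With complete data the post-therapy contrast is unbiased, and chance imbalance is already in its standard error.
- A reader might infer that the 8 conditional items will be answered by different kinds of patient in each arm. This is plausible, since section 7.1 suggests a seven-day continuous infusion for Arm B and allows subcutaneous azacitidine for Arm A. But those regimens are not mandatory, setting is left to the treatment protocol or physician, and the form is completed after therapy. No setting-by-arm figure is given, so the size is unknown.
- A reader might want new scales built from the other 21 items. The documents contain no item-to-scale map, so it cannot be shown that those items form intact scales.

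**Conclusion.** The point holds for the change analysis. As scheduled, an HDC29 standardized response mean covers only pre-transplant to Day 100 in transplanted patients, and it cannot measure change due to IC or HMA. The between-arm comparison of post-therapy scores survives without a baseline, but less precisely: about 0.72 SD detectable at 30 per arm, against 0.69 to 0.52 SD with one. Those figures rest on the assumed correlation, α and power, and on all 60 patients completing the form.

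The unbiasedness also depends on complete forms, which death, withdrawal or not reaching transplant may prevent. Timing may differ too. If the form is completed at response assessment, that is about day 28 in Arm B but after 4 to 6 azacitidine cycles in Arm A, or 112 to 168 days at 28 days per cycle. A baseline reading does not cure either problem. The 8 setting-dependent items are a real gap in the scoring rules, of unknown size. Overall this is an inexpensive improvement, not a flaw in the primary analysis.

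**What to change.** **Preferred.** In sections 7.3 and 11.3 and Appendix D, add HDC29 at screening alongside the QLQ-C30. Use the items applicable before treatment and leave out the hospital and home blocks (44–47 and 56–59). In section 13, compare post-therapy HDC29 scores between arms adjusted for that baseline.

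**If HDC29 is not added at screening.** In section 13, limit the standardized response mean for the effect of initial therapy to the QLQ-C30. Specify a cross-sectional between-arm HDC29 comparison at the post-therapy reading. Label the pre-transplant to Day 100 HDC29 change as describing the transplant period in transplanted patients only.

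**In both cases.** Keep the module's own published scales. Report any scale or item that depends on items 44–47 or 56–59 descriptively, by setting.

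**Cost.** The preferred route adds about 21 items at a visit where the QLQ-C30 is already completed, a few of them less meaningful before therapy. The fallback changes only text and asks nothing more of patients.
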